16.1.5.2. Metabolic TEAEs

Metabolic TEAEs will be summarized. These will be identified with by using a list of specified terms from medical personnel.

16.1.6. SUBGROUP ANALYSIS OF ADVERSE EVENTS

A single summary of adverse events will be produced separated by the subgroups specified in section 7.5. Other adverse event summaries split by country are noted in the appropriate sections.

16.1.7. ADDITIONAL AE SUMMARIES

- Summary of AEs by combined terms
- Summary of AEs occurring in $\geq 3\%$ of subjects. This summary will be repeated separated by country.
- Summary of AEs by exposure at earliest onset.
- Summary of AEs by preferred term by descending frequency

Document: K:\DSP\SM-13496\KVA95374\Biostatistics\Documentation\SAP

Author: [REDACTED]

Version Number:

1.0

Version Date:

30MAR2017

Template No: CS_TP_BS016 – Revision 3

Reference: CS_WI_BS005

Effective Date: 01May2012

Copyright © 2012 [REDACTED] All rights reserved.

The contents of this document are confidential and proprietary to [REDACTED]. Unauthorized use, disclosure or reproduction is strictly prohibited.

There will be no statistical comparisons between the treatment groups for safety data, unless otherwise specified with the relevant section.

16.1. ADVERSE EVENTS

Adverse Events (AEs) will be coded using Medical Dictionary for Regulatory Activities (MedDRA) central coding dictionary, Version 19.1.

Treatment-emergent adverse events (TEAEs) are defined as AEs with a start date on or after the date of first dose through 7 days after study drug discontinuation (14 days for serious adverse events and deaths) or through the last double-blind dose date for patients continuing into the extension study. All AEs with an onset date after the consent date for the extension study but prior to the first dose in the extension study will be summarized separately in the extension study. Adverse events and serious adverse events (SAEs) with completely missing onset dates will be summarized as treatment emergent regardless of severity or relationship to study medication, unless the AE stop date occurs before the treatment start date.

See Appendix 2 for handling of partial dates for AEs. In the case where it is not possible to define an AE as treatment emergent or not, the AE will be classified by the worst case; i.e. treatment emergent.

An overall summary of patients within each of the categories described in the sub-section below, will be provided as specified in the templates.

Listings will include TEAEs and Non-TEAEs.

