6.4.1.3 Collection and recording of adverse events

AEs will be collected for each patient from the time the informed consent is obtained until the last study visit. Patients should be queried in a non-leading manner, without specific prompting (eg, "Has there been any change in your health status since your last visit?"). AEs and SAEs will be monitored throughout the study at all visits.

All AEs should be collected and recorded in the patient's study records/source documents, in accordance with the investigator's normal clinical practice, and in the eCRFs.

Each AE will be evaluated for duration, severity, seriousness, action taken with the study treatment, outcome, and causal relationship to the study treatment. Definitions for severity, action taken with the study treatment, outcome, and causal relationship to the study treatment are presented below. When the severity of an AE which has an onset before the treatment phase worsens after the initiation of the treatment phase, the more severe AE should be captured as a new AE.

Severity of AE

- **Mild** – Ordinarily transient symptoms that do not influence performance of patient’s daily activities. Other treatment is not ordinarily indicated.
- **Moderate** – Marked symptoms sufficient to make the patient uncomfortable. Moderate influence on performance of patient’s daily activities. Other treatment may be necessary.
- **Severe** – Symptoms cause considerable discomfort. Substantial influence on patient’s daily activities. May be unable to continue the study, and other treatment may be necessary.

When the severity of an AE changes, the maximum severity for the event should be noted.

The action taken with the study treatment:

- **Drug Withdrawn** – Study drug stopped permanently.
- **Dose Reduced**
- **Dose Increased**
- **Dose Not Changed**
- **Not Applicable**

The outcome of the AE:

- **Recovered/Resolved**
- **Recovering/Resolving**
- **Not Recovered/Not Resolved**
- **Recovered/Resolved with Sequelae**
- **Fatal**
- **Unknown**

The causal relationship of the AE to the study treatment:

- **Not related**
 - **Not related** – Improbable temporal relationship and is plausibly related to other drugs or underlying disease.
 - **Unlikely** – occurred within a reasonable time frame after administration/discontinuation of the study drug, but there is a likely association of an intercurrent/underlying medical condition or other drugs.

- Related

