9.7 Safety analysis

9.7.1 Adverse events

The summary of AEs will be limited to treatment-emergent AEs (TEAEs), which are defined as AEs with onset on or after Day 1. An ADR will be defined as an AE related to the study treatment; an AE of which causality with study drug is related, probably related or possibly related.

The number and percentage of patients with at least one AE or ADR for each preferred term and system organ class will be summarized by treatment group. This summary will be repeated for death, SAEs, AEs leading to the study discontinuation, severe AEs, and extrapyramidal AEs.

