6.3. DERIVED TIMEPOINTS

6.3.1 LOCF Timepoint

The last non-missing post-baseline measurement collected within the double-blind treatment phase will be carried forward and will be defined as the Week 6/last observation carried forward (LOCF) endpoint record. Measurements eligible for LOCF endpoint will be restricted to post-baseline measurements through either the Week 6 visit day (for patients entering the long term study) or 7 days after double-blind study drug discontinuation (for discontinued patients not entering the open-label phase). Unscheduled visits are considered useable for derivation of the LOCF endpoint in all domains.

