16.3.2. LABORATORY REFERENCE RANGES AND MARKEDLY ABNORMAL CRITERIA

Quantitative laboratory measurements will be compared with the relevant laboratory reference ranges and categorized as:

- Low: Below the lower limit of the laboratory reference range.
- Normal: Within the laboratory reference range (upper and lower limit included).
- High: Above the upper limit of the laboratory reference range.

In addition to the high and low quantitative laboratory assignments (as identified by means of the laboratory reference ranges), markedly abnormal quantitative safety (and other) laboratory assessments will also be identified. Markedly Abnormal Post-baseline Laboratory Values (MAPLV) for selected laboratory parameters can be found in Table C. The criterion of MAPLV is satisfied if a value falls into the markedly abnormal range. Patients will be represented in the count of a particular MAPLV if they have experienced that MAPLV at least once during the post-baseline double-blind phase, regardless of baseline value, up to and including LOCF endpoint. The number and percentage of patients with MAPLV will be presented by treatment group and for the combined SM-13496 group.

Table C: Criteria for Markedly Abnormal Post-Baseline Laboratory Values

Hematology Parameter	Markedly/Abnormal Range
Hemoglobin	Male: ≤ 11.5 g/dL Female: ≤ 9.5 g/dL
Hematocrit	Male: ≤ 37% Female: ≤ 32%
WBC	≤ 2.8 x 10 ⁹ /L ≥ 16 x 10 ⁹ /L
Neutrophils (percent)	≤ 15%
Eosinophils (percent)	≥ 10%
Platelet Count	≤ 75 x 10 ⁹ /L ≥ 700 x 10 ⁹ /L
Clinical Chemistry Parameter	Markedly/Abnormal Range
Alkaline Phosphatase	≥ 3 x ULN

Document: K:\DSP\SM-13496\KVA95374\Biostatistics\Documentation\SAP
 Author: [REDACTED] Version Number: 1.0
 Version Date: 30MAR2017

Template No: CS_TP_BS016 – Revision 3 Reference: CS_WI_BS005
 Effective Date: 01May2012

Copyright © 2012 [REDACTED] All rights reserved.
 The contents of this document are confidential and proprietary to [REDACTED] Unauthorized use, disclosure or reproduction is strictly prohibited.

ALT	≥ 3 x ULN
AST	≥ 3 x ULN
Total Bilirubin	≥ 2.0 mg/dL
Albumin	< 50% LLN
Glucose (fasting)	< 45 mg/dL >160 mg/dL
Sodium	< 130 mmol/L > 150 mmol/L
Potassium	< 3 mmol/L > 5.5 mmol/L
Chloride	< 90 mmol/L > 115 mmol/L
Calcium	< 8.4 mg/dL > 11.5 mg/dL
Blood Urea Nitrogen	≥ 30 mg/dL
Creatinine	≥ 2.0 mg/dL
Creatine Phosphokinase	≥ 3 x ULN
LDH	≥ 3 x ULN
HbA1c	≥ 7.5%
Prolactin	≥ 5 x ULN
Total Cholesterol (fasting)	≥ 300 mg/dL
LDL Cholesterol (fasting)	≥ 200 mg/dL

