A composite measure of suicidality measures the presence of any suicidal ideation or behavior. The number and percentage of subjects with suicidality as measured by the C-SSRS will be summarized and compared among the SM-13496 treatment groups versus placebo using Fisher's exact test, where suicidality is defined as having at least one occurrence of suicidal ideation or at least one occurrence of suicidal behavior. The baseline suicidality indicator will be set to 1 if the subject exhibits suicidality during the two weeks prior to the baseline visit, 0 if the subject does not exhibit suicidality during the two weeks prior to the baseline visit, and missing otherwise. The post-baseline suicidality indicator is similarly defined for each post-baseline weekly visit. This analysis will be performed at Week 6, LOCF endpoint, and overall (based on all post-baseline visits up to and including LOCF endpoint) by treatment group and combined SM-13496 group.

An overall summary of post-baseline data across all visits up to and including LOCF endpoint will include the frequency and percentage of the following by treatment group and for the combined SM-13496 group:

- At least one suicidal ideation post-baseline
- No suicidal ideation post-baseline
- Emergence of suicidal ideation (no suicidal ideation at baseline, and any type of suicidal ideation post-baseline)
- Emergence of serious suicidal ideation (no suicidal ideation at baseline, and any serious suicidal ideation [ideation score of 4 or 5] post-baseline)
- Most severe type of ideation post-baseline
- Worsening of suicidal ideation (most severe suicidal ideation post-baseline was more severe than it was at baseline)
- At least one suicidal behavior post-baseline
- No suicidal behavior post-baseline
- Emergence of suicidal behavior (no suicidal behavior at baseline, and any type of suicidal behavior post-baseline)
- At least one actual attempt post-baseline
- At least one interrupted attempt post-baseline
- At least one aborted attempt post-baseline
- At least one preparatory act or behaviors post-baseline
- At least one instance of suicidality [any ideation or behavior] post-baseline
- No suicidality post-baseline

Document: K:\DSP\SM-13496\KVA95374\Biostatistics\Documentation\SAP

Author: [REDACTED]

Version Number:

1.0

Version Date:

30MAR2017

Template No: CS_TP_BS016 -- Revision 3

Reference: CS_WI_BS005

Effective Date: 01May2012

Copyright © 2012 [REDACTED] All rights reserved.

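### For patients continuing into the extension, SAP 16.1 closes the TEAE window at the last double-blind dose, so an adverse event starting on the Week 6 visit day is normally in no TEAE table of this study

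*SAP*

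**What the plan says.** SAP 16.1 classifies AEs by start date. For patients who do not continue, the TEAE window runs to 7 days after discontinuation, or 14 days for serious AEs and deaths. For the others it runs "or through the last double-blind dose date for patients continuing into the extension study", with no days added. To the extension, a hand-over sentence then passes "All AEs with an onset date after the consent date for the extension study but prior to the first dose in the extension study". SAP 16.1 also states: "Listings will include TEAEs and Non-TEAEs".

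Other parts of the plan draw the line later:

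- Protocol 6.4.1.3: "AEs will be collected for each patient from the time the informed consent is obtained until the last study visit".
- Protocol 9.7.1 limits AE summaries to TEAEs, "which are defined as AEs with onset on or after Day 1", and gives no end date.
- Protocol 9.3.2, repeated in SAP 6.2, takes post-baseline data for analysis through 7 days after the final dose.
- SAP 6.3.1 lets the last-observation-carried-forward (LOCF) endpoint use measurements "through either the Week 6 visit day (for patients entering the long term study". The markedly abnormal laboratory counts in SAP 16.3.2 run "regardless of baseline value, up to and including LOCF endpoint", and the overall C-SSRS suicidality summary in SAP 16.7.4 uses the same end point.

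SAP 3.3 states that nothing in the analysis was changed from the protocol.

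**The concern.** The AE tables stop earlier than the laboratory and suicidality tables for the same patients, and earlier than either protocol definition allows. The day normally lost is the day of the final assessments.

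Two kinds of event could be missed. The first is an AE dated to a Visit 8 finding. In completers, body weight, ECG, fasting glucose and lipids have no other scheduled post-baseline measurement (protocol 6.4.2 to 6.4.4), and clinically significant findings are recorded as AEs (protocol 6.4.1.2). The second is a manic AE first dated at Week 6. A first YMRS score of 16 or more at the last visit cannot satisfy the two-consecutive-assessments limb of SAP 16.7.5, so only the TEAE limb could identify that patient.

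At stake is a modest undercount of AEs in the randomized comparison, together with a departure from the protocol that is not declared.

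**Working it through.** **Where the last dose falls.** Let V be the Week 6 visit day, L the date of the last double-blind dose, and g = V − L.

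- The drug is taken once daily after the evening meal (protocol 5.2.1).
- Visit 8 blood is drawn after a fast of at least 10 hours (protocol 5.5), and Visit 8 assessments follow the final dose by no more than 72 hours (Table 1, footnote a).
- The pharmacokinetic sample is taken 13 to 15 hours after a dose on the day before the visit (Table 1, footnote i). Only consenting patients give this sample; for the others the timing is inferred.
- Double-blind drug is dispensed at Visits 2 to 7 and at unscheduled visits, not at Visit 8 (protocol 5.2.2).

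So g is normally 1. Since 72 hours after an evening dose is the evening of L + 3, g is at most 3.

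**Is an AE with known onset on V a TEAE?** The conditions are V ≤ L for a continuing patient; V ≤ L + 7 for a non-continuing patient, and likewise under the protocol 9.3.2 window; and V ≥ Day 1 under protocol 9.7.1.

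| g | Continuing, SAP 16.1 | Not continuing, SAP 16.1 | Protocol 9.3.2 window | Protocol 9.7.1 | Days left out if continuing |
|---|---|---|---|---|---|
| 0 | yes | yes | yes | yes | 0 |
| 1 | no | yes | yes | yes | 1 |
| 2 | no | yes | yes | yes | 2 |
| 3 | no | yes | yes | yes | 3 |

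Only a double-blind dose dated on the visit day itself (g = 0) keeps the event.

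**Does another sentence recover it?** The worst-case rule in SAP 16.1 applies when treatment emergence cannot be determined, and Appendix 2 deals with partial or missing dates. A known onset date is neither. The hand-over sentence requires onset after the extension consent date. If consent is dated V, an onset on V is not covered; if consent is dated V − 1 or earlier, an onset before the first extension dose goes to the extension study. Neither case puts it in a TEAE table here. Because the two boundaries (last dose date and consent date) are independent, they can also overlap when consent precedes the last dose.

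**Size.** Visit 8 falls on Day 39 to 45. As a fraction of the days from first dose through the visit:

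- one day: 1/45 = 2.2% to 1/39 = 2.6%;
- three days: 3/45 = 6.7% to 3/39 = 7.7%.

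These are calendar fractions, not shares of AEs.

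The 28 pooled centers in SAP Table B sum to 524 patients (target 501). SAP 15.1.4.2 gives about 82% completers and a 17.4% dropout rate: 524 × 0.82 = 430, and 524 × (1 − 0.174) = 433. How many completers continue is not stated. Assuming 60%, 80% or 100% of 430, the shorter window applies to about 258, 344 or 430 patients. If Table B leaves out unpooled centers, these figures are too low.

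**The case against.** The strongest defence is attribution. AEs are classified by date, and protocol 6.4.1.3 does not list onset time among the attributes to be evaluated. If the first extension dose is taken on the visit day, a cut at the last double-blind dose ensures that nothing arising after extension drug is credited to a randomized arm, placebo included. That aim is sound, but it can be met by excluding onsets known to follow the first extension dose, without giving up the whole visit day.

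The examples are also conditional. Patients are asked about changes since the last visit, so symptoms reported at Visit 8 may carry an earlier onset and count. Laboratory and ECG findings are read centrally; if onset is dated to receipt of the report, even a window ending on the visit day would miss them. The mania case further requires a patient still deemed eligible to continue. Visit 8 laboratory, QTc and weight values remain in their own tables whatever happens to the AE. All of this stands and limits the size of the effect.

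A reader might infer that these events are lost altogether. The documents do not support that: they are listed, and the extension may count them. A reader might also infer that every upper limit in SAP 16.1 is an undeclared change. The 7-day limit is not, because protocol 9.3.2 already sets it. Protocol 9.3.2 does not rescue the limit for continuing patients, which is shorter.

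**Conclusion.** The point holds and is minor. For continuing patients the TEAE window normally stops one day, and at most three days, before the end of the Week 6 visit day. A known visit-day onset is then absent from this study's TEAE tables. That disagrees with protocol 9.3.2, protocol 9.7.1 and SAP 6.3.1, and SAP 3.3 does not declare it.

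The effect is likely small. It would be tempting to read the rule as biasing the comparison, but it is the same in every arm and nothing in the documents shows a difference between arms. Nor does SAP 16.1 expressly say that the cut-off overrides the 14-day limit for serious AEs in continuing patients; that is the natural reading of the sentence, no more.

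The conclusion assumes the usual evening dose on the day before the visit. The number of patients under the rule assumes that Table B covers all randomized patients. The number of AEs affected, the number of patients continuing and the extension's own counting rules cannot be determined from these documents.

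**What to change.** In SAP 16.1:

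- Run the TEAE window for continuing patients through the Week 6 visit day, the boundary SAP 6.3.1 already uses for them, excluding onsets known to be after the first extension dose. A visit-day onset before that dose is then a TEAE for every g from 0 to 3.
- Where the first extension dose is on the visit day and no onset time is recorded, assign the AE to one study at the blinded data review, before unblinding.
- Align the hand-over sentence with the extension plan so that each AE is counted in exactly one study.
- Say whether the rule for continuing patients covers serious AEs.

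In SAP 3.3, list as changes from the protocol only the limit for continuing patients and the 14-day limit for serious AEs and deaths.

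The cost is a few sentences, one derivation, coordination with the extension plan and a manual check of untimed same-day onsets. AE counts may rise slightly. Unequal follow-up remains, since non-continuing patients are still followed for 7 days, or 14 for serious AEs and deaths.

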16.1.1. ALL TEAEs

Incidence of TEAEs will be presented by System Organ Class (SOC) and Preferred Term (PT) and also broken down further by maximum severity and relationship to study medication. This summary will be repeated separated by country.

16.1.1.1. Severity

Severity is classed as mild/ moderate/ severe (increasing severity). TEAEs starting after the first dose of study medication with a missing severity will be classified as not specified. If a subject reports a TEAE more than once within that SOC/ PT, the AE with the worst case severity will be used in the corresponding severity summaries. In determining maximum severity, response values will be ranked in order from minimum severity to maximum severity as values: 'not specified', 'mild', 'moderate', and 'severe'.

16.1.1.2. Relationship to Study Medication

Relationship, as indicated by the Investigator, is classed as related or not related. The categories of 'possible', 'probable', and 'definite' will be pooled to create the 'related' category. Similarly, 'not related' and 'unlikely' will be pooled to create the 'not related' designation. If a subject has more than one AE within an SOC and preferred term, the subject will be counted once according to the highest relationship. Adverse events with missing relationship will be classified as 'not specified'. In determining highest relationship, response values will be ranked in order from minimum relationship to maximum relationship as values: 'not specified', 'not related', and 'related'.

Document: K:\DSP\SM-13496\KVA95374\Biostatistics\Documentation\SAP

Author: [REDACTED]

Version Number:

1.0

Version Date:

30MAR2017

Template No: CS_TP_BS016 – Revision 3

Reference: CS_WI_BS005

Effective Date: 01May2012

Copyright © 2012 [REDACTED] All rights reserved.

The contents of this document are confidential and proprietary to [REDACTED]. Unauthorized use, disclosure or reproduction is strictly prohibited.

16.2. DEATHS

If any patients die during the study, the information will be presented in a data listing. Deaths will be recorded on the AE panel as an AE leading to death

16.3. LABORATORY EVALUATIONS

Results from the central laboratory will be included in the reporting of this study for Hematology, Blood Chemistry and Urinalysis. Endocrine parameters will be summarized separately. A list of laboratory assessments to be included in the outputs is included in Table 6 of the protocol.

A LOCF endpoint will also be derived for laboratory evaluations. For calculation details, please see section 6.3.

Presentations will use reported units.

Quantitative laboratory measurements reported as "< X", i.e. below the lower limit of quantification (BLQ), or "> X", i.e. above the upper limit of quantification (ULQ), will be converted to X for the purpose of quantitative summaries, but will be presented as recorded, i.e. as "< X" or "> X" in the listings.

The following summaries will be provided for laboratory data:

- Baseline and change from baseline by visit (for quantitative measurements)
- Incidence of abnormal values according to normal range criteria (Urinalysis parameters only)
- Shift from baseline according to normal range criteria (for quantitative measurements and categorical measurements)
- Summary of subjects meeting markedly abnormal criteria (for quantitative measurements and categorical measurements)
- Listing of patients meeting markedly abnormal criteria

Additionally, the change from baseline value at LOCF endpoint for selected laboratory parameters will be evaluated using a nonparametric rank ANCOVA. For each pairwise comparison versus placebo, values of the change from baseline at LOCF endpoint and baseline values will be ranked. A linear regression will be conducted on the change from baseline ranks with baseline value rank as independent variable to produce regression residuals. Using the values of the residuals as scores, Mantel-Haenszel row mean score tests will be produced for each SM-13496 group versus placebo (Stokes, Davis, & Koch, 1995). This will be conducted for prolactin, glucose, HbA1c, and lipid tests (HDL cholesterol, LDL cholesterol, total cholesterol, and triglycerides), glycoalbumin, and HOMA-IR. Prolactin will be assessed separately by sex.

The following parameters are presented split by fasting status and overall: HDL cholesterol, LDL cholesterol, total cholesterol, insulin, triglycerides, glucose and HOMA-IR. For laboratory variables split by fasting, change from baseline will only be calculated where the post-baseline fasting status matches the baseline fasting status.

Document: K:\DSP\SM-13496\KVA95374\Biostatistics\Documentation\SAP
Author: [REDACTED] Version Number: 1.0
Version Date: 30MAR2017

Template No: CS_TP_BS016 – Revision 3
Effective Date: 01May2012.

Reference: CS_WI_BS005

Copyright © 2012 [REDACTED]. All rights reserved.
The contents of this document are confidential and proprietary to [REDACTED]. Unauthorized use, disclosure or reproduction is strictly prohibited.

